2.0 STUDY OBJECTIVES

Hypothesis: We hypothesize that PROMISE will lead to a reduction in the percentage of pediatric patients ages 3-7 who require general anesthesia use for daily radiation treatment from 70% (historical control) to 30%.

2.1 Primary Objectives

- 2.1.1 To decrease the total number of pediatric patients who require general anesthesia through the use of PROMISE.

2.2 Secondary Objectives

- 2.2.1 To assess the impact that PROMISE has on patient/family anxiety and quality of life, treatment time and clinical efficiency, and overall cost.
- 2.2.2 To determine the average patient movement and beam stoppages with PROMISE.

2.3 Endpoints

- 2.3.1 Primary: The percentage of pediatric patients age 3-7 who require daily general anesthesia for all treatments, compared to historical control. (Correlates with Primary Objective 2.1.1)
- 2.3.2 Secondary: Secondary outcomes will be measured comparing those who successfully are treated using PROMISE for any fraction vs. those who require general anesthesia for all fractions. (Correlates with Secondary Objective 2.2.1)
 - Patient/family-reported health quality of life, assessed using PedsQL 3.0 Cancer Module.
 - Patient anxiety, measured by the modified Yale Preoperative Anxiety Survey Short Form (mYPAS-SF).
- 2.3.3 Exploratory: Exploratory outcomes will also be measured comparing those who successfully are treated using PROMISE for any fraction vs. those who require general anesthesia for all fractions. (Correlates with Secondary Objectives 2.2.1 and 2.2.2).
 - Treatment time per fraction.
 - Workflow data: treatment time, average patient movement (magnitude, vertical, longitudinal, lateral, yaw, roll, and pitch), the number beam turn offs due to movement beyond threshold and total time out of tolerance.
 - Cost savings.

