| RECIST | Response Evaluation Criteria in Solid Tumors |
| SAE | Serious Adverse Event |
| SAbr | Stereotactic ablative body radiotherapy |
| SBRT | Stereotactic body radiotherapy |
| SCCC | Simmons Comprehensive Cancer Center |
| scRNAseq | Single cell RNA sequencing |
| SGOT | Serum Glutamic Oxaloacetic Transaminase |
| SPGT | Serum Glutamic Pyruvic Transaminase |
| TRUS | Transrectal ultrasound |
| WBC | White Blood Cells |

STUDY SCHEMA**Primary Endpoint & Hypothesis**

- Percentage of Children Ages 3-7 Requiring General Anesthesia: We hypothesize that PROMISE will lead to a reduction in the percentage of patients **ages 3-7** who require general anesthesia during radiation treatment from **70%** (institutional historical control) to **30%**.

Secondary Endpoints

Secondary endpoints will be analyzed for those on trial treated with PROMISE vs. anesthesia.

- Patient/family-reported health quality of life (PedsQL 3.0 Cancer Module) and anxiety (mYPAS-SF).
- Workflow data: treatment time, average patient movement, and number of beam turn offs due to movement beyond threshold.
- Overall cost of treatment.

STUDY SUMMARY

| | |
|--|--|
| Title | Pediatric Radiation Oncology with Movie Induced Sedation Effect (PROMISE): A Phase II Clinical Trial to Safely Reduce Anesthesia Use |
| Short Title | PROMISE Clinical Trial to Reduce Anesthesia Use |
| Protocol Number | STU-2021-1005 |
| Phase | Phase II |
| Methodology | Single-arm, open label |
| Study Duration | 2 years |
| Study Center(s) | Single-center |
| Objectives | 
Primary: To decrease the total number of pediatric patients who require general anesthesia through the use of PROMISE.
 
Secondary:
 
 - To assess the impact that PROMISE has on patient/family anxiety and quality of life, treatment time and clinical efficiency, and overall cost. - To determine the average patient movement and beam stoppages with the use of PROMISE. |
| Number of Subjects | 30 |
| Diagnosis and Main Inclusion Criteria | Age 3-11 and planned to undergo radiation therapy. |
| Study Product(s), Dose, Route, Regimen | PROMISE: an audio/visual technology for children to focus on during each radiation treatment to prevent movement. |
| Duration of administration | PROMISE will be used for each fraction of radiation treatment; number of fractions will vary by patient depending on individual diagnosis and treatment plan. |

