 - If patient cannot successfully complete PROMISE, second treatment will be scheduled and planned similar to the first treatment, in a 60-minute slot with patient NPO and anesthesia on standby.
 - If second treatment is also not successful, no more attempts will be made with PROMISE and remaining treatments will be done under general anesthesia.
 - If the second treatment is successful, third treatment will be performed similarly.
 - If third treatment is successful, remaining treatments will be with PROMISE only, in 30-minute slots without anesthesia on standby.

- If third treatment is not successful, no more attempts will be made with PROMISE and remaining treatments will be done under general anesthesia.
- For each treatment session, the following workflow data will be measured: 1) total treatment time, 2) average patient movement (VisionRT), 3) number of beam turn offs due to movement beyond threshold (VisionRT).

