5.2.2 Radiation Treatment

- For the first treatment, a 60-minute slot will be scheduled. Patient will be instructed to be kept NPO for 6 hours and anesthesia will be available on stand-by. Patient will be immobilized with PROMISE, and treatment will be attempted.
 - If patient successfully completes treatment with PROMISE, future treatments will be scheduled in 30-minute slots without anesthesia available on standby

If patient cannot successfully complete PROMISE, the second treatment may be scheduled and planned similar to the first treatment at treating physician's discretion, in a 60-minute slot with patient NPO and anesthesia on standby, or patient can proceed with anesthesia for subsequent treatments. The patient may continue subsequent treatments with anesthesia at the physician's discretion..

- At the treating physicians discretion, the same procedures undertaken on Day 1 may be attempted a week later (+/- 7 days) if PROMISE was previously unsuccessful. By this time, many patients will potentially be calmer and more accustomed to treatment, a new environment, etc. and more likely to tolerate PROMISE.

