5.2.3 At Each Treatment

- For each radiation treatment session, the following workflow data (as applicable) will be measured for all patients: 1) total treatment time, 2) average patient movement (VisionRT), and 3) number of beam turn offs due to movement beyond threshold (VisionRT).

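### Workflow data are collected per fraction but compared by child, so the two arms of the 2.3.3 comparison mix modes; movement and beam-offs with PROMISE would probably be understated, and the effect on treatment time cannot be signed

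*Combined protocol and SAP*

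**What the plan says.** - **Collection, section 5.2.3:** "For each radiation treatment session, the following workflow data (as applicable) will be measured for all patients". The items are total treatment time, average movement and number of beam turn-offs. The footnote to the table in 5.4 adds total time out of tolerance.
- **Objective, section 2.2.2:** "To determine the average patient movement and beam stoppages with PROMISE".
- **Comparison, section 2.3.3 (exploratory):** the outcomes are to be measured "comparing those who successfully are treated using PROMISE for any fraction vs. those who require general anesthesia for all fractions". One of them is "Treatment time per fraction". The section links these outcomes to objectives 2.2.1 and 2.2.2; no other endpoint serves 2.2.2.
- **Study Schema:** workflow data are listed as secondary, with a looser grouping: "Secondary endpoints will be analyzed for those on trial treated with PROMISE vs. anesthesia".
- **Routes to a mixed course:** section 4.1 describes a failed first session, a successful second, and then "If third treatment is not successful, no more attempts will be made with PROMISE and remaining treatments will be done under general anesthesia". Section 1.3 moves a child to anesthesia after two consecutive noncompliant fractions unless the physician directs otherwise. Section 5.2.2 says that "the same procedures undertaken on Day 1 may be attempted a week later (+/- 7 days) if PROMISE was previously unsuccessful".
- **Failed attempts in children who never succeed, section 4.1:** "If second treatment is also not successful, no more attempts will be made with PROMISE and remaining treatments will be done under general anesthesia".
- **Analysis, section 9.3:** only interim reports are described. Nothing says how fractions of different modes within one child are to be handled.

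**The concern.** The measurement unit is the fraction and the grouping unit is the child. One successful PROMISE fraction puts a child in the PROMISE group, so the fractions that child later (or earlier) received under anesthesia go there too. A child whose attempts all end in anesthesia is in the anesthesia group, and the attempted PROMISE sessions go with that child. Failed attempts of a crossover child stay in the PROMISE group.

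Objective 2.2.2 asks how much children move, and how often the beam stops, with PROMISE. The stated grouping does not measure that. It matters because section 4.2 names movement during the beam as the only toxicity that could be linked to PROMISE, even indirectly, and section 7.2.1 says acute and late adverse events are not captured. The workflow data are therefore a main source on positional accuracy in awake children, alongside automatic beam-off and the reporting of serious or PROMISE-attributed events under section 7.3.

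This is separate from whether the two groups of children are comparable. It would arise even if they were.

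**Working it through.** The plan states no figure for the workflow comparison, so there is none to reproduce.

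**1. Composition of a course.** Section 1.1 gives 25 to 30 fractions as common. On the section 4.1 route of failure, success, failure, then anesthesia:
- completed with PROMISE: 1/30 to 1/25 = 3% to 4%
- failed attempts: 2
- anesthesia with no attempt: 22/25 = 88% to 27/30 = 90%

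All of these fractions belong to a PROMISE-group child. A child with two failed attempts and then anesthesia has 2/30 to 2/25 = 7% to 8% of fractions that were PROMISE attempts, all in the anesthesia group.

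**2. Movement illustration.** The documents give no movement values, so these inputs are assumed:
- 30 children with 30 fractions each. Nine never succeed (the hypothesized 30%, stated for ages 3-7, applied to all 30), with 2 failed attempts each.
- c = 1 to 5 crossover children on the route above; the other 21 − c complete every fraction with PROMISE.
- Movement units: 1.0 for completed PROMISE, 3.0 for a failed attempt, 0.2 under anesthesia.

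A crossover child's total is 3 + 1 + 3 + 27 × 0.2 = 12.4.

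PROMISE mean by child = [30(21 − c) + 12.4c] / 630
- c = 1: 612.4/630 = 0.97
- c = 5: 542/630 = 0.86

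PROMISE mean over attempted fractions = [30(21 − c) + 7c + 54] / [30(21 − c) + 3c + 18]
- c = 1: 661/621 = 1.06
- c = 5: 569/513 = 1.11

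Shortfall: 1 − 0.972/1.064 = 9% and 1 − 0.860/1.109 = 22%.

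Anesthesia mean by child = (2 × 3.0 + 28 × 0.2)/30 = 11.6/30 = 0.39, against 0.20 for fractions with no attempt. The gap between modes narrows from both sides.

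**3. Sensitivity to the number of failed attempts.** Children who fail at CT simulation may have no treatment attempt (4.1, 5.2.1), and 5.2.2 allows anesthesia after one failure.
- One attempt each: 634/612 = 1.04 (c = 1) and 542/504 = 1.08 (c = 5); shortfall 6% and 20%.
- None: 607/603 = 1.01 and 515/495 = 1.04; shortfall 3% and 17%.

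**4. Treatment time.** Assume 30 min for completed PROMISE and 60 min for a failed attempt (the slot lengths in 4.1), with g min for an anesthetized fraction and c = 3.

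By child: [18 × 900 + 3(150 + 27g)]/630 = (16,650 + 81g)/630. By attempted fraction: (16,200 + 450 + 1,080)/567 = 31.3 min.

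| g (min) | PROMISE by child (min) | By attempted fraction (min) |
|---|---|---|
| 20 | 29.0 | 31.3 |
| 30 | 30.3 | 31.3 |
| 45 | 32.2 | 31.3 |
| 60 | 34.1 | 31.3 |

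The sign changes at a g of about 35 min (5 crossover children) to 50 min (1 crossover child).

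**The case against.** **The plan defines groups of children, not an averaging rule.** Section 2.3.3 never says that anesthetized fractions enter a PROMISE mean, and objective 2.2.2 could be met by a sensible analyst using PROMISE sessions only. This stands in part: the averaging is an inference. But the grouping is stated, it is attached to a per-fraction outcome, and section 9.3 provides nothing to override it.

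**The qualifier in 5.2.3 may mean that movement is not recorded under anesthesia.** That does not rescue the comparison. The anesthesia group's movement data would then consist only of failed PROMISE attempts (mean 3.0 in the illustration). The PROMISE group would still lack those attempts: 607/603 = 1.01 against 1.06 with one crossover child, and 515/495 = 1.04 against 1.11 with five.

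**The outcomes are exploratory.** Section 2.3.3 labels them so, and no test, power calculation or decision rule depends on them. This stands and limits the weight of the point, although objective 2.2.2 is secondary and the Study Schema lists workflow data as secondary.

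**Stronger readings that a reader might infer, which the documents do not support:**
- *Time with PROMISE is understated as well.* Sections 1.1 and 1.2 describe visits with anesthesia as longer and cite a 38% shorter session with a similar device. If so, anesthetized fractions counted as PROMISE raise PROMISE time, while the misplaced failed attempts lower it.
- *All failed attempts are charged to anesthesia.* Only those of never-successful children are.
- *A child with one success has 29 of 30 fractions without movement, so an assumed 3 beam-offs per PROMISE fraction shrinks to a mean of 0.1.* The 4.1 route includes two failed attempts. At 3 beam-offs on each of three attempts the mean is 9/30 = 0.3, and that is one child, not the group.

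**Conclusion.** The concern holds for the workflow outcomes in 2.3.3. The stated grouping mixes modes in both directions and does not answer objective 2.2.2.

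For movement, beam-offs and time out of tolerance, the bias is toward understating PROMISE relative to anesthesia, provided movement is lowest under anesthesia and highest in failed attempts. The illustrated size is about 9% to 22% with two failed attempts per never-successful child, and 3% to 17% with none. These figures rest on assumed movement values and crossover counts and are not predictions.

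Treatment time is contaminated, but the direction cannot be determined: the length of an anesthetized session is not given, and it is not stated whether treatment time means beam, room or visit time.

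The primary endpoint, a per-child classification, is unaffected. The point is a worthwhile correction to an exploratory analysis that serves a secondary objective.

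**What to change.** For the workflow outcomes in 2.3.3, change the unit of comparison from the child to the fraction:

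1. At each session, record the mode attempted and the mode that completed the fraction.
2. Report movement, beam turn-offs, time out of tolerance and treatment time in three classes: PROMISE completed; PROMISE attempted, then converted or abandoned; anesthesia with no attempt. Let 'with PROMISE' mean the first two together, and show failed attempts separately as well.
3. Account for clustering by child, with a random child effect or per-child means within class.
4. Define treatment time by its start and end points.
5. Keep the by-child comparison for quality of life and anxiety, which are not measured per fraction. Align the Study Schema with 2.3.3 on grouping and on secondary or exploratory status.
6. Keep any within-child comparison of time descriptive, because session order and slot length (60 against 30 minutes) confound it.
7. Reconcile the retry provisions in sections 1.3, 4.1 and 5.2.2, which differ and determine how much mixing occurs.

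The cost is one or two extra fields per session and slightly more analysis work, with no new visits or patients. The fields should be added while the trial is running, because the mode of each fraction may be hard to reconstruct later.

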4.0 TREATMENT PLAN

4.1 Treatment Dosage and Administration

Pediatric Radiation Oncology with Movie Induced Sedation Effect (PROMISE) is an interactive, incentive-based movie system that integrates with a video surveillance gating module (VisionRT) to help keep a children's attention and prevent him or her from moving during radiation treatment. This technology is being studied as an alternative sedation solution for pediatric patients needing radiation treatment.

All patients on study will receive radiation treatment per standard of care for patient's diagnosis. The dose, fractionation, and possible concurrent treatments will all vary from patient to patient. Because we plan to enroll such a wide variety of patients, treatment will be unique for every patient. PROMISE will be consistent throughout the study, though, and attempted in every patient that can tolerate it.

The following protocol will be used to implement PROMISE for each patient:

- 1) Consultation:
 - During initial consultation with eligible patients, the clinical trial will be discussed and should they agree to participate, patients/families will be consented.
- 2) CT simulation session:
 - Initial screening for PROMISE will occur in CT simulation suite.
 - Patient will be instructed to be NPO for 6 hours, and anesthesia will be available as stand-by.
 - CT scan of region of interest, per standard clinical practice, will be attempted with modified version of PROMISE for audiovisual distraction, with patient under direct observation.
 - If the patient cannot comply with instructions of laying still for a few minutes for the CT scan, the attending radiation oncologist will be asked to re-evaluate the appropriateness of evaluating the child with PROMISE.
 - If PROMISE ultimately is unsuccessful, the patient will undergo general anesthesia for the CT simulation and subsequent treatments.
- 3) Treatment sessions:
 - For the first treatment, a 60-minute slot will be scheduled. Patient will be instructed to be kept NPO for 6 hours and anesthesia will be available on stand-by. Patient will be immobilized with PROMISE, and treatment will be attempted.
 - If patient successfully completes treatment with PROMISE, future treatments will be scheduled in 30-minute slots without anesthesia available on standby.

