5.1.8 Quality of life (QOL) questionnaires

Baseline patient/family-reported health quality of life (QOL), assessed using PedsQL 3.0 Cancer Module, and patient/family-reported anxiety, measured by the modified Yale Preoperative Anxiety Survey Short Form (mYPAS-SF), will be assessed. The PedsQL for the patient will be optional.

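### The secondary and exploratory comparisons set PROMISE successes against PROMISE failures, so they cannot be read as the impact of PROMISE

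*Combined protocol and SAP*

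**What the plan says.** The Study Summary describes the design as "Single-arm, open label", and Section 4.1 says PROMISE is "attempted in every patient that can tolerate it". Section 2.3.2 assesses PedsQL and mYPAS-SF by "comparing those who successfully are treated using PROMISE for any fraction vs. those who require general anesthesia for all fractions". Section 2.3.3 applies the same split to treatment time, workflow and cost savings. The Study Schema agrees ("Secondary endpoints will be analyzed for those on trial treated with PROMISE vs. anesthesia"), although it lists workflow and cost as secondary where 2.3.3 calls them exploratory.

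The comparison serves objective 2.2.1: "To assess the impact that PROMISE has on patient/family anxiety and quality of life, treatment time and clinical efficiency, and overall cost".

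Only the primary endpoint has a historical control. Section 9.3 covers interim reports and gives no model, covariate, age stratum or comparator for these outcomes. Baseline PedsQL and mYPAS-SF are collected (5.1.8), but no analysis uses them. On self-report, 5.1.8 adds: "The PedsQL for the patient will be optional".

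**The concern.** Both groups were offered PROMISE; what separates them is whether it worked. The protocol itself describes what decides that. Section 1.3 makes non-sedated treatment conditional on passing a movement test at simulation. Section 1.1 says the need for GA falls with age, yet ages 3-11 are pooled. Sections 5.2.1 and 5.2.2 leave several steps to the physician. Section 5.2.2 also expects calmer children to tolerate PROMISE better, and the activity item of the mYPAS-SF (Appendix C) scores restless movement, so the anxiety outcome overlaps with the behaviour that defines the groups.

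A gap in quality of life or anxiety may therefore reflect which children fail rather than what avoiding GA does for them. Read as impact, it could credit PROMISE with a benefit it did not produce.

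The any-fraction rule adds a second problem: a child treated partly with PROMISE and partly under GA counts wholly as PROMISE for time, beam stops and cost. Such children can arise by fail-success-fail under 4.1, by two later noncompliant fractions under 1.3, or by a retry a week later under 5.2.2.

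**Working it through.** **The plan's own figure.** No size or power is stated for any secondary or exploratory comparison. The only design figure is for the primary test (Section 9.2: n = 13, 70% versus 30%, two-sided exact binomial at 0.05, 84% power). It reproduces: rejecting at 5 or fewer GA children has probability 0.018 under 70% and power 0.835 under 30%. It supplies the inputs below but says nothing about the secondary contrasts.

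**Group sizes.** Section 9.2 expects 30 children, 13 of them aged 3-7, leaving 17 aged 8-11. At the 30% target, 13 × 0.30 = 3.9 young children fail. The documents give no GA rate for ages 8-11; assume 0-10% fail there, adding 0 to 1.7. Failures total 3.9 to 5.6, or 13% to 19% of 30. Children aged 3-7 then make up 70-100% of failures (3.9/5.6 to 3.9/3.9) but only 35-37% of successes (9.1/26.1 to 9.1/24.4).

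**Spurious gap, model A.** Let failing be the top fraction p of a normal propensity that correlates ρ with the outcome, and let the treatment method have no effect on the outcome. The gap is ρ × φ(k) / [p(1 − p)] in outcome SDs, with k the upper-p normal quantile.

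| Scenario | p | φ(k)/[p(1−p)] | Gap, ρ = 0.3 | Gap, ρ = 0.5 |
|---|---|---|---|---|
| PROMISE cuts GA as hoped, but outcome unaffected | 0.15 | 0.2332/0.1275 = 1.83 | 0.55 | 0.91 |
| PROMISE changes nothing, no older failures: 9.1/30 | 0.30 | 1.65 | 0.50 | 0.83 |
| PROMISE changes nothing, 20% of older fail: (9.1 + 3.4)/30 | 0.42 | 1.60 | 0.48 | 0.80 |

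The values of ρ and the 0-20% for older children are assumptions. The range is roughly 0.5 to 0.9 SD.

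**Spurious gap, model B.** A simulation with a distress trait that correlates separately with failure and with outcome, 30% failing at ages 3-7, 5% assumed at 8-11, and no effect on the outcome:

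- Trait correlations of 0.3, 0.5 and 0.7 give 0.14, 0.39 and 0.77 SD. These are smaller than model A because the implied failure-outcome correlation is the square (0.09, 0.25, 0.49).
- A 0.5 SD age difference in the outcome alone gives 0.24 SD.
- Trait at 0.5 plus the age difference gives 0.62 SD, and an unadjusted t-test rejects 23% of the time against a nominal 5%.

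**Precision.** The 95% half-width is t(28) × √(1/n₁ + 1/n₂).

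- 4 versus 26: 2.048 × 0.537 = 1.10 SD.
- 6 versus 24: 2.048 × 0.456 = 0.93 SD.
- Ages 3-7 only, 4 versus 9: 2.201 × 0.601 = 1.32 SD.

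At the target rate, the chance of 2 or fewer failures among the 13 young children is 20%.

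**The case against.** **Time and cost.** GA itself lengthens visits (Section 1.1) and is costed in Section 1.2 at about $50,000 per child over a six-week course. Those differences are therefore not selection alone. This stands. They still do not estimate the effect of offering PROMISE, because both groups were offered it. Movement and beam stops also serve objective 2.2.2, which is descriptive.

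**Silence on adjustment.** A reader might infer that an unadjusted analysis was chosen. The documents do not say so: Section 9.3 specifies no secondary analysis of any kind. What they do fix is the pair of groups and the causal reading, and that is the fault.

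**Certainty.** A reader might infer that the plan would show a benefit even if PROMISE did nothing. That is too strong. The correlations are assumed, and at 4 versus 26 a true gap of 0.55 to 0.91 SD reaches p < 0.05 only about 17-37% of the time. Nor does any section state that failures start out more anxious; only the age gradient is documented directly. Exclusion 3.2.1 also removes some children who would certainly need GA.

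**Cost overstatement.** A reader might infer that savings would be inflated several-fold, since about 26 children would be labelled PROMISE while 13 × (0.70 − 0.30) = 5.2 young children avoid GA because of it. That requires crediting every PROMISE child with an avoided GA course. No section gives that rule, or any cost formula.

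**PedsQL forms.** The age forms are less of an obstacle than they look. The 5-7 child form uses 0/2/4 on the same 0-4 range, and parent forms cover every enrolled age. They are not identical, however: the cognitive scale has 5, 4 and 3 items for ages 8-12, 5-7 and 2-4.

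**Mixed-method children.** The documents give no frequency for them, so the size of that distortion is unknown.

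**Conclusion.** The concern holds for the comparison as defined. Sections 2.3.2 and 2.3.3 form groups by the result of the intervention, and 2.2.1 reads the difference as its impact. For quality of life and anxiety, a gap of roughly 0.5 to 0.9 SD (model A) or 0.14 to 0.77 SD (trait alone, model B) in favour of PROMISE is possible with no true effect. Both ranges rest on assumed correlations. The expected 95% half-width is about 0.9 to 1.1 SD, so the contrast is imprecise as well as biased. For time and cost, the difference mixes a real GA effect with selection and with the any-fraction labelling. The documents do not support a specific cost multiplier, or a claim that a favourable result is assured. The primary endpoint is not affected. This should be corrected before analysis.

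**What to change.** 1. Reword objective 2.2.1 and endpoint 2.3.2 as an association between treatment method and outcome. Analyse weekly parent-report PedsQL (as scale scores, because item counts differ by age form) and mYPAS-SF in all enrolled children, adjusted for baseline score and age, and show ages 3-7 as a subset. State that with about 4 to 6 failures, adjustment removes only part of the bias. Ages 3-7 should not be the main set, given the 1.32 SD half-width.
2. Analyse treatment time, movement and beam stops per session by the method actually used at that session, with a random effect for child. Section 5.2.3 already collects these data at each session.
3. Do not derive cost savings from the success-versus-failure contrast. For ages 3-7, report observed GA use against that expected from the 70% historical per-patient rate (13 × 0.70 = 9.1 children), with the unit cost stated as an assumption, since the schedule in 5.4 contains no cost item. Report ages 8-11 descriptively, because no historical rate is given for them.

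The cost is analysis wording plus a stated unit cost; no visits, children or clinical procedures change. The downside is that objective 2.2.1 claims less.
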